1.3. Study Objectives

The objective of this study is to evaluate the safety and effectiveness of implanting the HeartWare® HVAD System via thoracotomy in subjects at risk of death from refractory end-stage left ventricular heart failure, who receive the device intended as a bridge to cardiac transplantation (BTT).

2. Statistical Methods

2.1. Sample Size Estimate and Justification

2.1.1. Sample Size

Success at 6 months is estimated to be 86% compared to a performance goal of 77.5%. Using an exact binomial test, with a one-sided alpha of 0.05, and 80% Power, a sample size of 145 implanted subjects is required.

The target success estimate of 86% is based on the following:

- The primary endpoint observed in the final BTT IDE Report for the more recent BTT CAP population (N=242), resulted in a success rate of 85.8% (205 out of 239 eligible subjects) for sternotomy subjects.

- Post-approval data from the INTERMACS Registry (through Q2 2014), indicates similar results for the sternotomy population of 88.0% (396/450) with a lower rate of success for the small subset of thoracotomy (83.3%, 55/66) and thoracotomy on-pump (82.6%, 38/46) subjects.
- The INTERMACS Federal Partners Report (from Q1 2014) indicates an 85% Kaplan-Meier survival estimate at 6 months. This is not the same as “success” in that post-exchange survival is considered.

Success will be met if the lower bound of the upper one-sided exact 95% confidence interval is greater than 77.5%.

The mean length of initial hospital stay is estimated to be 26.1 days with a standard deviation of 22.8 days and a median of 20 days based on data from the BTT CAP population (N=242). Using a one sample t-test, with a one-sided alpha of 0.05, a sample of 145 implanted subjects with an average value of 21.3 days or less will result in power greater than 80%.

2.2. Patient Analysis Sets

There are two main analysis populations that will be used in results evaluation. These are the Intent-to-Treat (ITT) and Per-Protocol (PP) subject populations. All endpoints will be assessed on the ITT and PP populations.

2.2.1. Primary Analysis Set

The Per-Protocol (PP) subject population will include all ITT subjects who were implanted with the HVAD pump® via thoracotomy, on-pump, and with outflow to the ascending aorta and with no major protocol deviation.

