## 11. STATISTICAL CONSIDERATIONS

### 11.1 Study Endpoints and Hypotheses

#### 11.1.1 Analysis Populations

The Intent-to-Treat (ITT) subject population will include all enrolled subjects intended to receive the HVAD® pump via thoracotomy at the time of skin incision.

The Per-Protocol (PP) subject population will include all ITT subjects who were implanted with the HVAD pump® via thoracotomy, on-pump, and with outflow to the ascending aorta. Sample size requirements reflect the minimum number of subjects needed for the PP population.

The primary analysis population is the PP population. All endpoints will be assessed on the ITT and PP populations.

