### **13.6 Protocol Deviations and Medical Emergencies**

The Investigator will not deviate from the protocol without the prior written approval of HeartWare except in medical emergencies or in unforeseen, isolated instances where minor changes are made that will not increase the subject's risk or affect the validity of the study. In medical emergencies, prior written approval for protocol deviations will not be required, but HeartWare personnel must be notified via telephone within 24 hours of occurrence.

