1.1. List of Abbreviations

Abbreviation	Definition
ADE	Adverse Device Effect
AE	Adverse Event
ATC	Anatomical Therapeutic Chemical
BiVAD	Biventricular Assist Device
BMI	Body Mass Index
BSA	Body Surface Area (m ²)
BTT	Bridge to (Cardiac) Transplantation
CABG	Coronary artery bypass graft
CAP	Continuous Access Protocol
CCU	Coronary Care Unit
CI	Confidence Interval
CNS	Central Nervous System
CPB	Cardiopulmonary Bypass
CREB	Clinical Research Ethics Board
CT	Computed Tomography
CVA	Cerebral Vascular Accident (stroke)
DSMB	Data Safety Monitoring Board
Dy	Day / Days
ECMO	Extracorporeal Membrane Oxygenation
EuroQol (EQ)	European Quality of Life (EQ-5D)
GCP	Good Clinical Practice
GI	Gastrointestinal
HCVA	Hemorrhagic Cardiovascular Accident
ICF	Informed Consent Form
ICH	International Conference of Harmonization
ICU	Intensive Care Unit
ICVA	Ischemic Cardiovascular Accident
INTERMACS	InterAgency Registry for Mechanical Assisted Circulatory Support
IPD	Important Protocol Deviation
IRB	Institutional Review Board
ITT	Intent to Treat
KCCQ	Kansas City Cardiomyopathy Questionnaire (tool)
KM	Kaplan-Meier
LOS	Length of Stay
LV	Left Ventricle
LVAD	Left Ventricular Assist Device
MAP	Mean Arterial Pressure

Abbreviation	Definition
MRS (mRS)	Modified Rankin Scale
N or n	Number of Patients
NYHA	New York Heart Association (heart failure classification)
PMA	Pre-Market Approval
PP	Per Protocol
RVAD	Right Ventricular Assist Device
RVEF	Right Ventricular Ejection Fraction
SAS	Statistical Analysis System
SD	Standard Deviation
SE	Standard Error
TIA	Transient Ischemic Attack
UADE	Unanticipated Adverse Device Event
UCL	Upper Confidence Limit
VAD	Ventricular Assist Device
VAS	Visual Analog Scale
WHO	World Health Organization

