The Intent-to-Treat (ITT) subject population will include all enrolled subjects intended to receive the HVAD® pump via thoracotomy at the time of skin incision.

The Per-Protocol (PP) subject population will include all ITT subjects who were implanted with the HVAD pump® via thoracotomy, on-pump, and with outflow to the ascending aorta. Sample size requirements reflect the minimum number of subjects needed for the PP population.

Data recorded in the INTERMACS® database to the primary endpoint at 6 months post implant of the HeartWare® HVAD will be evaluated.

Subjects who remain on device support after the primary endpoint time-point, either the original device or exchange device, will be followed according to the INTERMACS® protocol until transplant, or until 5 years post implant of the original device. A subject's study participation is considered complete at either the time of induction of anesthesia for transplant, or at the 5 year post implant visit.

- Subjects who have been explanted for recovery prior to month 6 will be followed until their next scheduled follow-up visit according to the INTERMACS® protocol, at which time their participation in the study is considered complete.
- The per-protocol analysis population will include those thoracotomy subjects with the outflow in the ascending aorta only as well as those thoracotomy subjects with the procedure performed on-pump only. As a result, enrollment may exceed sample size requirements.

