2.4.5. Patient Disposition

Disposition of Subjects

The number of subjects enrolled, who received an implant, and who are evaluable will be summarized. The number of treated subjects who completed the study, the number of subjects who discontinued from the study and the reasons for discontinuing from the study will also be summarized.

Protocol Deviations

Important protocol deviations (IPD) as defined by the HeartWare review team will be reported and presented with the final analysis.

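### SAP 2.2.1 adds an undefined exclusion for major protocol deviations to the set that decides the 77.5% test; the protocol definition has no such condition

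*SAP*

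**What the plan says.** Protocol 11.1.1 restricts the PP set to ITT subjects who were "implanted with the HVAD pump® via thoracotomy, on-pump, and with outflow to the ascending aorta". It then states: "The primary analysis population is the PP population". SAP 1.2 repeats the same three conditions and ties the sample size to them: "on-pump, and with outflow to the ascending aorta. Sample size requirements reflect the minimum number of subjects needed for the PP population". The bullets on the PP population in the protocol's study summary and in its section 7.2 also carry no condition about deviations.

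SAP 2.2.1, under the heading for the primary analysis set, ends differently: "with outflow to the ascending aorta and with no major protocol deviation".

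The nearest SAP text on deviations is in 2.4.5 and uses another word: "Important protocol deviations (IPD) as defined by the HeartWare review team will be reported and presented with the final analysis". The SAP abbreviation list likewise has only "Important Protocol Deviation". Protocol 13.6 deals with approval and notification of deviations and does not grade them, though it expects some to arise in urgent situations: "In medical emergencies, prior written approval for protocol deviations will not be required".

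SAP 2.2 adds that "All endpoints will be assessed on the ITT and PP populations"; SAP 2.2.2 labels ITT the secondary set.

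**The concern.** The SAP's operative definition of the primary set departs from the protocol's, and the added condition cannot be applied from the text. *Major* is not defined. *Important* deviations are identified by the sponsor's review team for reporting, without criteria, timing or a stated link to PP membership. The three operative conditions are fixed at surgery. A judgement about a deviation can be made later, when the 6-month result may already be known.

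There is no control arm, so selective exclusion has nothing to cancel against. If excluded subjects are enriched for failures, the observed success rate rises against a fixed goal. Protocol 13.6 makes some link plausible, because a deviation made in a medical emergency may accompany a poor clinical course. Even without bias, a set built as the protocol describes and a set built from SAP 2.2.1 could give different primary results.

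**Working it through.** **Inputs.** Performance goal p0 = 0.775, expected rate 0.86, one-sided alpha 0.05, N = 145 (SAP 2.1.1; protocol 11.2). The criterion is an exact one-sided 95% lower limit above 77.5% (SAP 2.4.1). The 145 is the minimum for the PP set (protocol 11.1.1). The number of excluded subjects is not given; I take 1 to 5 as an assumption.

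**Step 1: reproduce the plan's figure.** The critical count r is the smallest value with P(X ≥ r | n, 0.775) ≤ 0.05. At n = 145, r = 121, the exact error is 0.0494, and power is P(X ≥ 121 | 145, 0.86) = 84.3%. At n = 144 power is 79.2%, and 145 is the smallest n from which power stays at or above 80% for every larger n checked (up to 299). The plan's 145 is reproduced.

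**Step 2: removals unrelated to outcome.** The same test is applied to fewer subjects.

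| Analysed n | Successes needed | Exact error |
|---|---|---|
| 145 | 121 | 4.9% |
| 144 | 121 | 3.4% |
| 143 | 120 | 3.7% |
| 142 | 119 | 4.1% |
| 141 | 118 | 4.5% |
| 140 | 117 | 4.9% |

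The error never exceeds 5%.

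**Step 3: removals related to outcome.** Start with X successes among 145 at a true rate of 0.775. Remove kf failures and ks successes, and retest X − ks out of 145 − kf − ks. The trial passes if X − ks reaches the critical count for the reduced n. For example, with kf = 2 and ks = 0 the reduced n is 143 and the critical count is 120, so the error is P(X ≥ 120 | 145, 0.775) = 0.0752.

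Worst case, where every removed subject is a failure:

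| Removed | Passes if X is at least | Type I error |
|---|---|---|
| 1 | 121 | 4.9% |
| 2 | 120 | 7.5% |
| 3 | 119 | 11.0% |
| 4 | 118 | 15.4% |
| 5 | 117 | 20.8% |

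Five removed, by the number of failures among them (critical count 117 of 140, so X must reach 117 + ks):

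| Failures among 5 | Passes if X is at least | Type I error |
|---|---|---|
| 0 | 122 | 3.1% |
| 1 | 121 | 4.9% |
| 2 | 120 | 7.5% |
| 3 | 119 | 11.0% |
| 4 | 118 | 15.4% |
| 5 | 117 | 20.8% |

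At a true rate of 77.5%, 5 × 0.225 = 1.1 failures would be expected among five subjects chosen without regard to outcome.

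**Step 4: an example near the boundary.**

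| Result | Exact lower limit | p | Decision |
|---|---|---|---|
| 120/145 | 76.8% | 0.075 | fails |
| 120/144 | 77.4% | 0.054 | fails |
| 120/143 | 78.0% | 0.037 | passes |

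Removing two failures reverses the decision.

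**The case against.** Several points can fairly be made for the plan.

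- Excluding major deviators is a conventional feature of a per-protocol set. That is so, but here the PP set is primary rather than supportive, and the protocol chose a definition based on operative facts alone.
- SAP 1.2 is only a protocol summary, so an analyst would follow 2.2.1. This weakens the charge that the SAP contradicts itself. It leaves the mismatch with protocol 11.1.1 and the undefined term.
- *Major* may simply mean *important*, as judged by the sponsor's review team. The SAP does not say so, and *important* has no criteria or timing either.
- Parts of SAP 2.4.7 and protocol 11.4 are redacted, so a definition there cannot be fully ruled out. Those sections cover additional analyses and missing outcomes, which are unlikely places for it, and a definition would not remove the departure from the protocol.
- The study has few procedures of its own: protocol 9.2 names only the extra consent. Many possible deviations, such as consent or eligibility, would precede the outcome. This makes strong enrichment for failures less likely. By chance, three or more failures among five would occur about 8% of the time at a true rate of 77.5%, so the upper end of the range needs a real link to outcome.
- Shrinking from 145 is one setup. If enrolment exceeds 145 so that 145 remain after removing 1 to 5 failures, the error is P(X ≥ 121 | 145 + k, 0.775) = 6.9%, 9.5%, 12.5%, 16.2% and 20.5%. The picture is similar, but even one removal then matters.
- ITT results and important deviations are both reported, so a divergence would be visible. This is a genuine safeguard, but it does not change which set decides.

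**Conclusion.** The concern holds and should be fixed. The textual point is certain: SAP 2.2.1 adds a condition that protocol 11.1.1 and SAP 1.2 lack, and no readable text defines it. The effect on error is conditional. It is nil if exclusions are unrelated to outcome. With 145 subjects it ranges from 7.5% to 20.8% if two to five subjects are removed and all are failures, and it passes 5% once two of five removed subjects are failures. These figures assume a true rate of 77.5% and an exclusion count of 1 to 5 that the documents do not supply. They show what the wording permits and are no evidence that biased exclusion took place.

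**What to change.** Delete the deviation clause from SAP 2.2.1, so that the primary set matches protocol 11.1.1 and SAP 1.2. If an analysis without major deviations is wanted, keep it as a labelled sensitivity analysis. For that analysis, list the disqualifying deviations in the SAP, use one term for them throughout, and classify subjects before database lock without knowledge of the 6-month outcome. Leave the PP decision rule and the planned ITT analysis as they are.

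Listing and pre-classifying the deviations while keeping the clause would also limit the discretion, but the SAP would still differ from the protocol; deletion deals with both.

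The cost is SAP wording: one clause, plus a short list if the sensitivity analysis is kept. No new data are needed, and the sample size stands. The downside is that subjects with serious deviations stay in the primary set, and the estimate may be slightly less favourable.

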2.2.2. Secondary Analysis Set

The Intent-to-Treat (ITT) population will include all enrolled subjects intended to receive the HVAD® pump via thoracotomy at the time of skin incision.

2.2.3. Selection of Control Patients

This is a single arm study wherein all subjects are implanted via thoracotomy with the HeartWare HVAD® System. No active control is used.

2.3. Interim Analysis

Section 11.5 of the protocol states that an interim analysis would be performed when the first 100 subjects completed 6 months of follow-up. No such analysis was performed. Since any change to the final alpha level would be considered negligible (0.001), there will be no effect on final endpoint analyses.

2.4. Analysis

The following section outlines the general statistical methods to be performed for efficacy and safety analysis.

No adjustments for multiplicity will be performed.

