The success rate in this cohort will be statistically compared to the performance goal (77.5%) using an exact binomial test. Success will be met if the lower bound of the one-sided exact 95% confidence limit is greater than 77.5%.

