2.4.2. Secondary Endpoint

The secondary endpoint is improvement in the length of initial hospital stay (initial recovery and step down unit) for all enrolled and implanted subjects, which is calculated by considering the number of days in acute care (ICU/CCU) plus the number of days in intermediate/step-down care (both variables taken as reported directly by INTERMACS), comprising the total number of days post-implant to discharge.

It is estimated that the mean length of initial hospital stay is 26.1 days for median sternotomy patients and thus the relevant hypotheses for this endpoint for each cohort are given by

$$H_0: \mu_T \geq 26.1$$

$$H_a: \mu_T < 26.1$$

where μ_T = the mean length of initial hospital stay for the Thoracotomy Implant Technique of the HVAD.

This secondary endpoint will be calculated and tested for each cohort using an upper tail one-sided t-test at 0.05 level of significance. Due to the skewed nature of this data, a one-sample sign test with an upper tail one-sided level of confidence of 0.05 will be conducted as supportive analysis.

The number and percentage of subjects with re-hospitalization after the initial hospitalization will be tabulated. Cumulative length of re-hospitalization after initial hospital stay (LOS) overall will be summarized using descriptive statistics, including 95% confidence intervals for the means.

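### The two formal hypotheses are each tested at one-sided 0.05 with no stated order; a fixed sequence in SAP 2.4 would cap the chance of a false claim on either at a nominal 5%

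*SAP*

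**What the plan says.** SAP 2.4 opens the analysis section with "No adjustments for multiplicity will be performed". Two formal tests follow.

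- **Primary (SAP 2.4.1).** The null is a success proportion of 77.5% or less, tested by an exact binomial test. The decision rule is "Success will be met if the lower bound of the one-sided exact 95% confidence limit is greater than 77.5" (per cent). SAP 2.1.1 sizes the trial on it: "Using an exact binomial test, with a one-sided alpha of 0.05, and 80% Power, a sample size of 145 implanted subjects is required".
- **Secondary (SAP 2.4.2).** The null is a mean initial stay of 26.1 days or more, the alternative a shorter mean. "This secondary endpoint will be calculated and tested for each cohort using an upper tail one-sided t-test at 0.05 level of significance". SAP 2.1.1 gives it a power statement too: "a sample of 145 implanted subjects with an average value of 21.3 days or less will result in power greater than 80" (per cent).

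Nothing in SAP 2.4.2 makes the second test depend on the first, and neither do the protocol's study summary and section 11.2. The body of protocol 11.1.3 (Secondary Endpoint) is not visible and much of SAP 2.4.7 is blacked out, so the absence of an order is a statement about the visible text only.

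The rest of the plan adds no confirmatory test. SAP 2.4.3 makes the other endpoints descriptive, the sign test on stay is supportive, and SAP 2.3 reports that the planned interim look was not done. SAP 2.2 has every endpoint assessed in both the Intent-to-Treat (ITT) and Per-Protocol (PP) populations. PP is the primary set (protocol 11.1.1, SAP 2.2.1).

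**The concern.** Length of stay has its own null, alpha and power statement, which sets it apart from the descriptive endpoints. A shorter stay is also one of the benefits the protocol offers as a reason for the technique (sections 4.1 and 12.1), so a significant result would naturally be reported as a finding. The plan does not say what such a result means if the primary endpoint is missed.

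That combination would be hard to read in this trial. The visible text does not say how a death before discharge enters the stay, and protocol 11.4 rules out imputation of missing stays. If early deaths end the count or drop out, they would lower primary success while leaving the mean stay shorter or unpenalised.

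At stake is the error rate of a second claim, not the validity of the primary one.

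**Working it through.** **Inputs.** Primary: null 0.775, design value 0.86, n = 145, one-sided 0.05 (SAP 2.1.1, 2.4.1). Secondary: null mean 26.1 days, SD 22.8, design mean 21.3, n = 145, one-sided 0.05 (SAP 2.1.1, 2.4.2). The documents state no family-wise error figure and no correlation between the endpoints; the correlations below are assumptions.

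**1. The plan's own figures.**
- Primary: with n = 145 the smallest count whose upper tail under 0.775 is at most 0.05 is 121. The attained size is 0.0494, the exact lower limit at 121/145 is 77.52%, and power at 0.86 is 0.843. At n = 144 power is 0.792, and no larger n in the scan (up to 399) falls below 80%. So 145 is the smallest n from which power stays at or above 80%, and the stated sample size is reproduced.
- Secondary: the standard error is 22.8/√145 = 1.893, and the noncentrality is (26.1 − 21.3)/1.893 = 2.535. Power from the noncentral t distribution with 144 degrees of freedom is 0.810, which agrees with the stated figure of above 80%. This takes the test in the direction of the alternative (mean below 26.1).

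**2. Chance of at least one false claim as written, both nulls true, stay claim allowed regardless of the primary.**
- Independent tests: 1 − (1 − 0.05)² = 0.0975.
- With the attained binomial size: 1 − (1 − 0.0494)(1 − 0.05) = 0.0970.
- Bound under any dependence: 0.05 + 0.05 = 0.10, or 0.0994 with the attained size.
- Bivariate normal test statistics, nominal 0.05 each:

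| Assumed correlation | At least one false claim |
|---|---|
| −0.5 | 9.99% |
| 0 | 9.75% |
| 0.3 | 9.3% |
| 0.5 | 8.8% |
| 0.8 | 7.5% |

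**3. Fixed sequence: primary at 0.05, then stay at 0.05 only if the primary is met.**
- Both nulls true: a false claim requires rejecting the primary, so the error is at most 0.05 (0.0494 attained).
- Only the primary null true: the error is that of the primary test, at most 0.05.
- Only the stay null true: the error is at most that of the stay test, nominally 0.05.

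**4. What the sequence costs under the design alternatives.** A formal stay claim now needs both tests to succeed.
- Independent endpoints: 0.8428 × 0.8101 = 0.683.
- Lowest possible: 0.8428 + 0.8101 − 1 = 0.653.
- Highest possible: the smaller of the two powers, 0.810.

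For comparison, splitting alpha at 0.025 each would require 123 successes and cut primary power to 70.8%, with stay power at 71.2%.

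**The case against.** The strongest reply is that there is one primary endpoint, the only explicit success rule is attached to it, and its error is 5% whatever happens to the secondary. That stands. A reader might infer that the trial's main claim is exposed to an error of nearly 10%; it is not.

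A reader might also infer that the SAP permits a positive claim after a failed primary. The text does not go that far. SAP 2.4.2 gives hypotheses and a test but no rule on how the result is to be used, so such a claim is neither granted nor forbidden. The defect is that silence.

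The 9.75% is also conditional. It needs true success of 77.5% or less, while the rates cited in SAP 2.1.1 lie between 82.6% and 88.0%. If the primary null is false, the only error left is that of the stay test itself, and a gate does not change that. This stands too, and it is why the point is a modest one.

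Finally, the SAP states its choice openly, and with only two tests a reader can apply the hierarchy unaided. That lowers the importance but does not remove the case for writing the rule down, especially as stay is to be assessed in two populations and in cohorts that the visible text does not define.

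**Conclusion.** The point holds as a cheap improvement. The visible plan leaves two formal tests at one-sided 0.05 without an order. If stay may be claimed regardless of the primary, the chance of at least one false claim is 9.75% when both nulls are true and the tests are independent. It is 10% at most, and 7.5% to 9.3% over assumed positive correlations of 0.8 down to 0.3. A fixed sequence brings this to a nominal 5%.

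A reader might take the sequence to be free. It is free for sample size, alpha and primary power, but not for the secondary endpoint, where the chance of a formal claim falls from 81.0% to about 68% under independence.

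Two matters are separate and are not cured by a gate. The tail named in SAP 2.4.2 does not match an alternative of a shorter mean. And the 5% size of the t-test is itself nominal: simulation with n = 145 and assumed skewed shapes (gamma, and two lognormals matched to the stated mean with either the SD or the median) gave a size of about 6.7% to 8.3%.

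**What to change.** In SAP 2.4, replace the sentence on multiplicity with:

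> Mean length of initial hospital stay will be tested at one-sided 0.05 in the Per-Protocol population only if the primary endpoint is met in the Per-Protocol population; otherwise it, and in all cases the ITT and other cohort results for length of stay, will be reported descriptively.

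Naming the population matters. Without it, SAP 2.2 and 2.4.2 would still allow several stay tests at 0.05 after the gate opens.

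The cost is one sentence, and no formal length-of-stay claim if the primary endpoint is missed. The sample size stays at 145, both alphas at 0.05 and primary power at 84.3%.

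SAP 2.3 speaks of the interim look in the past tense, so the SAP may have been written late; the documents do not show whether results were known by then. If they were, apply the sequence as a reporting rule in the study reports and label it as added afterwards.
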